Intervention and survey progression. After the baseline survey, participants will be asked to download the app using their email and a password, so we can track their registration and ultimately link app use with survey data (e.g., to check number of sessions responded engaged in). We will incentivize the app download with a small e-gift card (\$10). Once registered, the app will randomize participants and they can immediately begin their first intervention sessions (NWC or counterfactual). Once participants have progressed through their respective programs, each will be given an additional small e-gift card (\$10), and, 2 months later, a URL for the first posttest. Similarly, at 6 and 12 months after program completion, each will be sent URLs to complete a survey.

We will regularly monitor electronic reports of progress through the intervention (for NWC), and survey completion progress for follow-up (both arms). Survey data will be routinely checked by the Data Management team for any problems, inconsistencies, or missing data. They will routinely summarize response rates for each survey, and by arm. If response rates are low, or unbalanced by arm, Drs. [name] and [name] will identify possible causes, their solutions, and quickly implement changes to rectify deficiencies.

D. Recruitment

The primary method of recruitment will be through multiple social media platforms. Specific recruitment activities will vary across the platforms, but will typically include posts to promote the program and study. We will also use seed recruitment, and encourage AIAN young women participants to invite their peers and family members to sign up for the program (i.e., chain referral, up to 3).

We will ask the participants enrolled in the study to follow our page on Instagram, share our recruitment post on their Instagram page and tag us in that post. This strategy will amplify our recruitment post among their followers (who may be similarly eligible) and encourage participation in our study (as the recruitment post will have come from a trusted source). This is completely voluntary and the recruitment post does not require participants to disclose any personal health information.

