G. Data Analysis Plan:

All intervention effectiveness analyses will be based on an intention-to-treat approach. For continuous outcomes (frequency/quantity indices of alcohol) and mediational outcomes (alcohol and contraceptive self-efficacy), we will estimate a series of latent growth curve models (LGCM) in Mplus to assess the effect of intervention exposure on the trajectories of those outcomes over the study period. The "normative" trajectory of an outcome is estimated for the comparison group before estimating the same trajectory among those exposed to the intervention. The third step estimates the degree to which the normative growth trajectory is altered by intervention exposure. On the fourth and final step, the interaction between intervention exposure and pre-intervention status on the outcome is tested. This permits an assessment of the differential effectiveness of the intervention as a function of baseline levels of the outcome variable.

For dichotomous outcomes, Latent Markov Models (LMM) will be used to evaluate transitions between behavioral states (e.g., sexually active to abstinent) throughout follow-up. 166,167 Intervention status is modeled as a time-invariant covariate; its effect on the transition probabilities is estimated freely. Effectiveness is indicated if those in the intervention have significantly lower probabilities than the controls of transitioning out of the abstinence state and significantly higher probabilities of transitioning out of the sexually active state. LMM may also reveal that early sexual experience among control group participants predicts sexual activity across the course of the study but that this relationship is interrupted among intervention participants. Other moderators of intervention effectiveness will also be explored (e.g., enculturation).

H. Summarize Knowledge to be Gained:

If successful, the overall study will generate evidence of NWC effectiveness for AEP prevention by demonstrating: 1) increased effective contraceptive use or sexual abstinence among urban AIAN young

women; 2) decreased or eliminated alcohol use in urban AIAN young women who drink; and 3) maintained abstinence (sexual or alcohol) among those who have this as their goal. If successful, the project will also provide vital information about the feasibility of mHealth interventions for reaching urban AIAN young women or other urban AIAN populations who might otherwise not access health information or interventions

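### The rule for dichotomous outcomes rests on transition contrasts that, after the first follow-up, start from post-randomisation states, and no arm contrast in all randomised women is defined

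*Combined protocol and SAP*

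**What the plan says.** Section IV.G (Data Analysis Plan) opens with a general principle: "All intervention effectiveness analyses will be based on an intention-to-treat approach". For dichotomous outcomes it specifies latent Markov models to "evaluate transitions between behavioral states (e.g., sexually active to abstinent) throughout follow-up". On how arm enters the model it says: "Intervention status is modeled as a time-invariant covariate; its effect on the transition probabilities is estimated freely". It does not say whether free estimation applies across intervals, across states, or both.

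The decision rule has two parts. The first concerns women who are abstinent: "Effectiveness is indicated if those in the intervention have significantly lower probabilities than the controls of transitioning out of the abstinence state". The second concerns women in the opposite state, for whom the NWC arm should show "significantly higher probabilities of transitioning out of the sexually active state". Neither part names an interval or a baseline stratum, and no rule combines the intervals. Neither this section nor any other gives an arm comparison of the proportion in a state at a fixed survey among all randomised women.

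On timing, section IV.C (Intervention and survey progression) places randomisation after the baseline survey: "Once registered, the app will randomize participants and they can immediately begin their first intervention sessions". Follow-up starts after program completion, with, "2 months later, a URL for the first posttest", and then "at 6 and 12 months after program completion, each will be sent URLs to complete a survey". That makes three follow-up surveys. The payment text under Procedures/modes of data collection in the same section counts a first post-intervention survey plus three follow-ups, which makes four.

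**The concern.** Randomisation balances the arms among women who are in a given state at baseline. It does not balance them among women who are in that state at a later survey, because NWC is meant to change who is there. If NWC moves the most changeable women early, those still sexually active in the NWC arm are on average harder to move. Their later exit probability can then be lower than in controls although no individual's later behaviour differs between arms.

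The rule treats all transitions alike. A real benefit could therefore go uncredited in later intervals, or be described as fading. Sexual activity, abstinence and effective contraceptive use are listed among the primary outcomes (section IV, Outcome Measures). Section IV.H promises evidence of increased contraceptive use or abstinence, which is a statement about how many women are in a state. The transition rule does not estimate that directly.

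**Working it through.** The documents give no transition rates, effect size, alpha or allocation ratio, so there is no figure of theirs to reproduce. All rates below are assumptions.

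**Which transitions start before randomisation.** Three follow-ups give three transitions: baseline to 2 months, 2 to 6, and 6 to 12. Only the first starts from a pre-randomisation state, so two of three are affected. On the payment text's count it is three of four.

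**Illustration 1: women sexually active at baseline, no return to activity.** Half are stayers (exit 5% per interval) and half are movers. Movers' first-interval exit is p = 0.20 in control and 0.40 in NWC. Their later exit is 0.30 in both arms, so the true effect is confined to interval 1.

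- Share still active after interval 1: 0.5(1 − p) + 0.5 × 0.95. Control 0.400 + 0.475 = 87.5%; NWC 0.300 + 0.475 = 77.5%. The benefit is 10 points.
- Exit in interval 2: [0.5(1 − p) × 0.30 + 0.475 × 0.05] / share still active. Control 0.14375 / 0.875 = 16.4%; NWC 0.11375 / 0.775 = 14.7%. The odds ratio is 0.88.
- Exit in interval 3: control 0.10656 / 0.73125 = 14.6%; NWC 0.08556 / 0.66125 = 12.9%.
- Still active at the end: control 62.5%, NWC 57.6%. The benefit is still 4.9 points.
- Pooled exit per interval at risk: control 0.37531 / (1 + 0.875 + 0.73125) = 14.4%; NWC 0.42431 / (1 + 0.775 + 0.66125) = 17.4%. The direction is right, but the contrast is 3.0 points against 10.0 (22.5% v 12.5%) in the randomised first interval.

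With movers' first-interval exit at 0.30 v 0.60, interval 2 gives 12.4% (NWC) v 15.6% (odds ratio 0.77), and pooling gives 20.9% v 15.9%.

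**Illustration 2: movement both ways.** Baseline abstinence is set at 31%, as 1 − 69%, where 69% is the background section's figure for high-school girls who have ever had sex. There are two equal types: one leaves abstinence at 40% and activity at 5% per interval, the other the reverse. The effect is in interval 1 only (× 0.5 on leaving abstinence, × 1.5 on leaving activity).

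| Interval | Leaving abstinence, NWC v control | Leaving activity, NWC v control | Share abstinent at end, NWC − control |
|---|---|---|---|
| 1 | 11.3% v 22.5% | 33.8% v 22.5% | +11.2 points |
| 2 | 15.3% v 14.8% | 15.1% v 17.4% | +6.2 points |
| 3 | 12.5% v 11.8% | 12.3% v 14.0% | +3.4 points |

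Both later contrasts change sign while abstinence is higher on NWC at every survey. If the effect is instead sustained in every interval, the contrast on leaving activity still shrinks, from +11.3 to +5.2 to +1.7 points.

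**Range and checks.** With weaker heterogeneity (30%/10%), the interval-2 shifts are only +0.1 points (leaving abstinence) and −0.7 points (leaving activity). With stronger heterogeneity and effect (60%/5%; × 0.25 and × 1.5) they are +3.9 and −8.9. With no heterogeneity, or with no effect, the later contrasts are exactly zero.

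**Test frequencies.** These come from a simulation of illustration 2 with 262 women per arm (half of the planned final 525). It assumed 1:1 allocation and two-sided 0.05, and used z tests on observed states rather than a fitted latent Markov model. A significant interval-2 difference against NWC on leaving activity occurred in 8.1% of runs in the main case and 47.9% in the strong case, against about 2.5% by chance. Pooled over intervals, it occurred in at most 0.2%.

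**The case against.** A reader might infer that the plan would report NWC as harmful. The text does not support that. The rule says when effectiveness is shown and contains no harm criterion; an unfavourable later contrast would at most withhold support. Nor does the text say that arm effects are tested interval by interval. If one arm effect covers all intervals, the examples above point the right way. A sign change needs interval-specific effects, unmeasured differences between women, and a real early effect. Under weak heterogeneity it is negligible. All of this stands, and it limits the point.

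A second defence is that every randomised woman can enter the likelihood under her assigned arm, so the intention-to-treat label is not empty, and that maintained abstinence, a goal in section IV.H, is naturally a conditional question. The first half is fair as to who is analysed, but it does not give later conditional contrasts a randomised interpretation. The second is met by conditioning on baseline abstinence, which keeps the randomised comparison.

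A third defence is that a latent Markov model handles misclassified states. It does, but that does not remove selection by unmeasured type, and the text specifies no mixture component. Section IV.G itself allows that early sexual experience may predict activity across the study, so differences between women are plausible here.

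**Conclusion.** The point holds in bounded form. Every transition after the first conditions on a post-randomisation state. The plan neither restricts the rule to the first transition nor says how intervals combine, and it defines no contrast of state prevalence among all randomised women. This follows from the text alone and is firm.

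The size is not firm, because every rate is assumed. Under moderate to strong heterogeneity with an early effect, interval-specific later contrasts shift against NWC by roughly 0.5 to 9 points while fewer NWC women are in the risk state. Under weak heterogeneity the shift is below 1 point. A pooled effect keeps its direction in illustration 1 but is diluted, and it mixes randomised with non-randomised comparisons. It would also be wrong to infer a raised false-positive rate: with no intervention effect the later contrasts are unbiased and type I error is not inflated. The risk is that a benefit goes uncredited or is misdescribed.

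**What to change.** In section IV.G, for each binary outcome, define the intention-to-treat effect as the arm difference in the probability of being in the state at a named follow-up (for example 12 months) among all randomised women. Estimate it directly, by a logistic or GEE model of state on arm and baseline state.

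Model-implied marginal probabilities from the latent Markov model are a substitute only if the arm effect is free in every interval and from each state. In illustration 1, a logistic transition model with interval-specific intercepts and one common arm effect implies 63.08% v 56.85% still active at the end. That is a difference of 6.2 points against the true 4.9.

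Keep the latent Markov model. State that baseline to first follow-up is the only transition contrast with a randomised interpretation, and label later ones descriptive. Reconcile the two survey counts in section IV.C, since they set how many transitions exist.

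The cost is a few sentences and no new data. The loss is that later transitions no longer count as evidence of effectiveness. With 525 of 700 women expected at the end, the direct model also needs a stated missing-data assumption.

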- SA2: **Translate AIY-C for mHealth delivery** through an iterative and theoretically driven process, integrating urban AIAN young women's input to enhance cultural and health engagement content and responsiveness; we will pilot and refine the translated mHealth AIY-C intervention.
- SA3: Recruit 700 (final N=525) urban AIAN young women using the refined social media strategies, and conduct an RCT to **rigorously evaluate the effectiveness of the mHealth translation of AIY-C** for preventing AEP and FASD.

SAs 1 and 2 were conducted under a separate COMIRB protocol (#18-0574) as preparatory to research efforts. For this protocol, we focus only on SA 3.

II. Background and Significance:

In the US, an estimated 1 in 8 pregnancies are exposed to alcohol.³⁸ In any given month, 2 million women, about 1 in 30, are at risk of AEP that could result in FASD.³⁹ FASD include FAS, partial FAS, alcohol-related birth defects, and alcohol-related neurodevelopmental disorders.⁴⁰ Children born with FASD suffer cognitive, physical, and social-emotional consequences throughout life; social and financial costs are enormous to individuals and society⁴¹⁻⁴⁶ Rates of drinking among pregnant AIAN women exceed those of other groups,⁴⁷⁻⁴⁹ with rates of 30%¹⁵-43%⁵⁰ in some samples. Prevalence estimates for FASD in AIAN communities are limited and often dated but exceed other groups by at least 2 or more times.^{48,51,52}

Given these data as well as a strong commitment to the health of future generations, tribal communities prioritize youth AEP prevention. AIAN youth are at-risk for initiating alcohol use at younger ages relative to their non-AIAN peers while patterns of use among AIAN youth who drink are more likely to put their own health and that of an unborn child at risk. High school AIAN girls are more likely to have drunk alcohol prior to age 13, currently drink, and drink 5+ drinks at a time compared to those in all other race groups. AEP data for AIANs are limited due to insufficient sample sizes in large national studies; however, the rates cited here confer risk for AEP when coupled with the early and unprotected sexual activity documented for AIAN youth. While over 70% of AIANs live in urban areas, little research exists on patterns of AEP among urban AIAN young women in particular. What does exist indicates that they may be at the same or greater risk for alcohol use and sexual risk compared to their non-AIAN counterparts.

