Studies/Progress Report: Adapted AIY-C intervention content. AIY-C integrates tribal values with guidance about young women's sexual health along with core messages about alcohol use and effective contraception from the original CHOICES curriculum. Given its applicability and relevance for all young women regardless of alcohol use or sexual activity, AIY-C adds messages to support young women who may choose to abstain from sex. Given AIY-C's focus on young women, messages about alcohol convey that no safe level of drinking exists for those under 21. In Table 3 we outline the AIY-C components (CHOICES core components) and their cultural, developmental. and universal adaptations that the CBPR methodology produced. We worked closely with our advisory

Table 3 AIY-C Selected components and adaptations

Table 3. AIY-C Selected components and adaptations		
	AIY-C Components	Cultural/ Developmental/Universal Adaptations
Session 1	Introduction: What is it? How does it	Relevance for young Native women, simplified
	work? How does it help?	language, scope of intervention broadened
	Reflection on 7 Teachings of Anishinaabe:	AIY-C specific cultural teachings emphasizing
	Love, honesty, respect, kindness, humility,	wellness and balance; reflections on
	bravery, wisdom	presence/absence/relevance of teachings
	Reflection on Medicine Wheel: Spiritual	AIY-C cultural heuristic emphasizing spiritual
	(North); Emotional (South), Physical (East),	wholeness and balance; participants asked to
	Mental (West)	reflect on alcohol's impact in key spiritual realms.
	Important Facts for Young Women: Safer	Simplified language, universal language about
	sex, birth control, and pregnancy	sex, condom use, safer sex practices, STD risks
	Daily Journaling: Instructions.	Online for security. added questions: offered
	,	drink/sex, safer sex practices, thoughts/feelings
Session 2	Personal Feedback: Alcohol risk, cost, and	Review of offers to drink, alcohol risk assessment
	calories	based on any drinking
	Personal Feedback: Birth control & safer	Review of offers to have sex, STD risk assessment
	sex, pregnancy, AEP, and STD Risk	
	Personal Goals: Alcohol	Continuing NOT to drink as goal for those who do
		not drink; cultural supports for goal attainment
	Change Ruler: Birth control & Safer sex	Added safer sex practices
	Personal Goals: Birth control & Safer sex	Continue NOT to have sex a goal for not sexually
		active, safer sex goals, cultural supports for goals

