NWC mobile app. Findings from our IDIs informed the content to include in our mobile app. The app contains six sessions; these sessions include content on alcohol use, birth control and safer sex, and facts of AEP and FASD. The app also includes culturally relevant imagery such as the medicine wheel and connections across generation. Motivational interview elements of tone, assessment of personal risk, decisional balance exercises, and goal setting are also included. Participant knowledge of alcohol and birth control methods, including condoms, is assessed through the app. See Appendix A for a selection of images from the App.

IV. Research Methods

We propose using an RCT with a baseline sample n=700 urban AIAN young women aged 16 to 20 to evaluate NWC for its effectiveness in AEP prevention.

Figure 1. NWC Conceptual Model

Outcome Measure(s): Figure 1 depicts the measures used the assess the impact of NWC. These measures include demographics, such as age, education level, and income, measures of social risk; environmental support; and cultural identity. Theoretical mediators include knowledge of effective contraception and alcohol use during pregnancy and self-efficacy related to sexual activity and contraceptive and alcohol use. Our primary outcomes include sexual activity, abstinence, effective contraceptive

use, and alcohol and other substance consumption—AEP protective and risk factors. With the pandemic, we have also added measures on experiences with COVID-19 to capture appropriate context.

B. Description of Population to be Enrolled:

Our population of focus will be AIAN women, ages 16-20, who live in urban areas (50,000 people or more), and who are not pregnant or breastfeeding at the time of enrollment. Currently, we are awaiting approval from the Southcentral Foundation of Alaska, a research review IRB for Alaska Native healthcare in

Anchorage (the only urban area in Alaska with population > 50,000). Until we receive this approval, we will exclude residents from Alaska.

C. Study Design and Research Methods

Screening

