We will screen each participant for eligibility before enrolling them into the study. The questions are administered by Qualtrics (accessed by URL from a recruitment flyer or social media post). These questions include items not on the recruitment advertisements as a way to screen out frauds - those who try to game the screening criteria to collect compensation. Each potential participant will provide answers to the following questions within the Qualtrics screening survey:

- 1. What is your assigned sex at birth?
- (if "other": What gender do you identify as?)
- 2. How old are you in years?
- 3. What is your race/ethnicity? Please select all that apply.
- 4. Are you currently pregnant?
- 5. Are you currently breastfeeding?
- 6. Do you currently live on an American Indian reservation or in an Alaska Native village?
- 7. What city do you live in?
- 9. In what state do you currently reside?

To be eligible for Native WYSE CHOICES, they must be: Biologically female, 16-20 years old, American Indian or Alaska Native (may identify with other races), not pregnant or breastfeeding, not living on a reservation, and living in an urban area (population >= 50,000). Because we do not yet have approval from the Native Alaska organization with oversight in Anchorage (the only Alaskan city to meet population size requirements), we will exclude Alaskan residents. Once a participant meets all eligibility criteria in the first part of the screener questions, they will be asked to enter their first name, cell phone number, email address, a second email address (optional) and birth month and year. The completed eligibility data are reviewed by a team member who will also check city population size. If all appropriate eligibility data are selected and the city named has a population of 50,000 or more, the participant is identified as "tentatively eligible." At this point, a member of the research team will reach out up to 4 times to confirm eligibility through a phone call or a text (for those youth uncomfortable with a phone call) by asking the respondent to confirm their name, birth month and year, city and state, and email address. This confirmation is short but provides an important opportunity to screen out frauds.

[figure not shown]

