Assignment methods. Once recruited and consented, eligible AIAN young women will complete the baseline survey, and asked to download the NWC app. Once they have done this, the app will immediately electronically randomize the participant to either NWC or the comparison condition. That is, the two interventions are accessed through the same app – once the participant registers to download the app, she will be randomly assigned one arm or the other. Figure 2 shows participant flow through the proposed project.

Progression of NWC. Because of the electronic mode of administration, participants can progress through each session at their own pace. We will provide electronic reminders if timely progression of the app has not been demonstrated.

Counterfactual intervention. We will provide young women in the comparison arm an engaging online intervention which is independent of our outcomes of interest. The focus will be on life skills including social media safety, budgeting, resume building, and career development.

Participant tracking methods. Participant tracking involves two sets of processes. The first is through screening and enrollment and then survey completion. The second centers on downloading the app and progression through the other surveys in a timely way. 1) On the screening survey, once participants are considered eligible, they will be required to provide their name, phone number, birth month and year, email address, and a second email address (optional). A second email is useful to keep in contact participants in case a primary email is closed. Once a participant has been determined eligible and has read and signed the consent form, we also request mailing address and social media handles, again, useful contact information to track participants over time since at this young age, contact information can change frequently. 2) During the registration process for the app, participants use an email address to register (the registration email is the link to the survey data, to track which participants downloaded and engaged in the app). Through the intervention stage, progress in NWC will be tracked electronically. We will send reminders to young women who have not completed a survey in a timely way (we allow 2 weeks). We will follow up with personal texts, emails, phone calls, or private social media contacts provided, up to 4 times, as necessary.

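### The effectiveness models use only arm and the outcome's own history; prespecifying baseline age, already collected before randomisation, would recover a modest amount of efficiency

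*Combined protocol and SAP*

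**What the plan says.** Section G (Data Analysis Plan) describes two model families.

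- **Dichotomous outcomes:** latent Markov models of movement between behavioural states over follow-up. Arm is the only covariate named: "Intervention status is modeled as a time-invariant covariate; its effect on the transition probabilities is estimated freely". Effectiveness is judged on the probabilities of leaving abstinence and of leaving sexual activity.
- **Continuous outcomes:** latent growth curve models, built in steps from the comparison-arm trajectory, the arm effect on it, and finally an interaction of arm with the pre-intervention level of the same outcome.

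The only other baseline variables mentioned there are moderators to be explored, with enculturation as the example.

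Age is available. The screening questions in section C include "How old are you in years", and women who pass the first part also give birth month and year. The Outcome Measure(s) paragraph of section IV lists "demographics, such as age, education level, and income" among the measures. Allocation comes later: after the baseline survey and app registration, "the app will immediately electronically randomize the participant to either NWC or the comparison condition". No stratification by age is described.

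**The concern.** Enrolment runs from 16 to 20, years over which drinking and sexual activity may well change. Two women who are both abstinent at baseline, one aged 16 and one aged 20, may differ in their risk of leaving that state, and the prior state cannot show this. If age predicts the outcome beyond its own history, leaving it out costs precision, by a different route in each model family.

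- In the linear growth models, variation explained by age stays in the residual and widens the standard error of the arm effect.
- In a logit transition model, the arm odds ratio is averaged over ages and lies closer to 1 than the age-conditional one. Adding age raises the standard error a little and the estimate by more, so power rises.

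The planned loss leaves a limited analysed sample ("Recruit 700 (final N=525) urban AIAN young women using the refined social media strategies"), and the value needed is already in hand.

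**Working it through.** **Sample size.** 700 × 0.75 = 525, so the two sample sizes agree with a 25% loss. That loss is implied by the same two figures, so this is no independent check. No alpha, power, effect size or age gradient is stated, so there is no power figure to reproduce. Everything below assumes two-sided 0.05, 1:1 allocation and 525 women analysed.

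**Continuous outcomes.** Set the detectable effect at 80% power with 525/2 = 262.5 per arm: (1.960 + 0.842) × √(2/262.5) = 0.245 SD. Let age correlate r_a with both the baseline and the follow-up outcome, and let baseline and follow-up correlate r_b. Then

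partial r = (r_a − r_a·r_b) / √[(1 − r_a²)(1 − r_b²)],

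and the standard error is multiplied by √(1 − partial r²). At the favourable end, r_a = 0.3 and r_b = 0.4: 0.18/√(0.91 × 0.84) = 0.206, so partial R² = 0.042.

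| r_b | r_a | Partial R² | SE cut | Power (from 80%) |
|---|---|---|---|---|
| 0.6 | 0.1 | 0.003 | 0.1% | 80.1% |
| 0.6 | 0.3 | 0.025 | 1.2% | 81.0% |
| 0.4 | 0.1 | 0.004 | 0.2% | 80.2% |
| 0.4 | 0.3 | 0.042 | 2.1% | 81.7% |

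The gain is 0.1 to 1.7 points.

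**One transition.** Simulated logistic regression as a stand-in for one transition of the Markov model, with the state treated as observed: 525 women all at risk, ages uniform over 16–20 and centred at 18, intercept −0.4, arm log odds ratio −0.5, 4,000 runs.

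| Age odds ratio per year | Without age: estimate (SE), power | With age: estimate (SE), power |
|---|---|---|
| 1.0 | −0.503 (0.1861), 78.0% | −0.504 (0.1865), 77.9% |
| 1.2 | −0.496 (0.1856), 76.8% | −0.504 (0.1875), 77.1% |
| 1.5 | −0.465 (0.1845), 72.2% | −0.503 (0.1918), 75.1% |

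Both parts of the mechanism are visible: without age the estimate shrinks toward 0, and with age the standard error rises by less than the estimate does. The squared ratio of the z values gives the effective sample size:

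- at 1.2, [(0.5041/0.1875)/(0.4957/0.1856)]² = 1.013;
- at 1.5, [(0.5029/0.1918)/(0.4654/0.1845)]² = 1.080.

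A second simulation looked only at leaving abstinence in the first interval (arm odds ratio 0.72, 2,000 runs). At 1.2, 1.4 and 1.6 per year the gain was about 1%, 3% and 6%. In a rerun with assumed intercepts, power barely moved: 16.2% to 16.1%, 15.1% to 15.2%, and 13.4% to 13.8%.

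**All transitions pooled.** 525 women, three intervals, arm odds ratio 0.72 per transition, assumed base rates, 1,500 runs. With the age odds ratio applied at every transition:

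| Age odds ratio | Gain in effective N | Power without → with age | Arm OR estimated without age |
|---|---|---|---|
| 1.2 | 4% | 73% → 75% | 0.72 |
| 1.4 | 13% | 64% → 70% | 0.74 |
| 1.6 | 22% | 60% → 69% | 0.75 |

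At 1.1 the gain is about 1%. The lower rows are steep. Compounded over three intervals, 1.2, 1.4 and 1.6 imply odds ratios of about 1.3, 1.6 and 2.0 per year of age for the state at 12 months.

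**The case against.** The strongest reply is that the models already contain the main prognostic information. A Markov transition is conditional on the previous state, and the growth models carry the outcome's own baseline. What age adds over a five-year range may be slight, and the documents give no figure for it. In a logit model the unadjusted odds ratio is a legitimate marginal quantity. Section G is also short, and Figure 1, the conceptual model, is not visible in the text available, so where it places demographics cannot be checked.

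All of this stands, and it limits the size of the point. It does not give age a role in section G, and exploring moderators is a different matter from adjusting the main contrast.

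Several stronger readings are tempting, and the documents do not support them.

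- **A biased comparison.** Randomisation protects the unadjusted contrast.
- **A transition model with nothing prognostic in it.** It conditions on the prior state.
- **A gain of 10–16% as the expected figure.** This arises when the 12-month state is tested given baseline, with age odds ratios of 1.4–1.6 at every transition. Section G's criterion is the transitions, and the 1.6 case takes control prevalence from about 18% at age 16 to 87% at 21 under assumed intercepts.
- **Protection against dropout bias.** Nothing shows that dropout depends on age, and age-related dropout alike in both arms does not in general bias the contrast.
- **A step in drinking at 21.** Section III reports the message that "no safe level of drinking exists for those under 21", but this describes the content of the predecessor intervention and is not evidence of an age effect. A separate indicator for age 20 would also be crude, since women pass 21 at different surveys.

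**Conclusion.** The point holds as one of efficiency and prespecification. Section G gives age no role in the main arm contrasts, although every randomised woman has supplied it.

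The gain rests wholly on assumed age effects:

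- about 1–6% in effective sample size for leaving abstinence, with 8% in the single-transition stand-in at 1.5 per year; over these single-transition calculations, about 0–3 points of power;
- more only if arm effects are pooled over all transitions and the age effect is steep;
- about 0.1–2 points of power for the alcohol indices with baseline included.

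If age is weakly related to outcome, almost nothing is gained or lost: at an age odds ratio of 1.0, power was 78.0% without age and 77.9% with it. The simulations treat states as observed, so they only approximate the latent model. The change is worth making because it is nearly free and its downside is negligible.

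**What to change.** In section G, before arm comparisons are seen:

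- derive baseline age as a continuous value from birth month and year;
- in the latent Markov models, enter it as a covariate on the initial state and on the transitions;
- in the growth models, enter it as a predictor of intercept and slope;
- take the main arm contrasts from these models, state that the transition odds ratios are conditional on age, and report the unadjusted contrasts alongside.

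The cost is one or two sentences and no new data. For a two-state outcome it adds three parameters if the age effect is held equal over intervals (one on the initial state, one on each of the two exits); a growth model with one slope gains two.
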